6.4.3 Trial discontinuation

The whole trial may be discontinued at the discretion of the primary investigator or the sponsor in the event of any of the following:

- Occurrence of AEs unknown to date in respect of their nature, severity and duration
- Medical or ethical reasons affecting the continued performance of the trial
- Difficulties in the recruitment of patients
- Cancellation of drug development

The sponsor and principal investigator will inform all investigators, the relevant Competent Authorities and Ethics Committees of the termination of the trial along with the reasons for such action. If the study is terminated early on grounds of safety, the Competent Authorities and Ethics Committees will be informed within 15 days.

7 Assessments

7.1 Assessment of efficacy

Efficacy will be evaluated through assessments of cardiac allograft vasculopathy; clinical events, blood tests of lipids, renal function, cardiac biomarkers, and inflammation; echocardiography; self-assessed quality of life; and cognitive function. All efficacy assessments will be made prior to administration of the first study drug dose, and at the end-of-treatment visit after twelve months. The results will be reported as baseline-adjusted between-group differences. Efficacy samples for the determination of blood lipids, renal function, and clinical events will be collected at 1, 2, 3, 6, 9, and 12 months, and analysed retrospectively. Cardiac biomarkers (NT-proBNP and TnT), will be analysed as safety parameters as well as efficacy parameters.

7.1.1 Intravascular ultrasound (IVUS)

Intravascular ultrasound examination of the same major epicardial coronary artery (preferentially the left-anterior descending coronary artery) will be performed during routine coronary angiography at 4 - 8 weeks after heart transplantation and at end-of-treatment one year after randomisation. In patients who have completed at least 6 months of study drug treatment, we will allow the second IVUS exam (used for assessment of the primary endpoint) to be performed at the time of study discontinuation for subjects who are unable to complete 12 months of treatment. All IVUS analysis will be conducted after trial closure by a core laboratory (Oslo University Hospital, Rikshospitalet, Oslo, Norway) by personnel blinded to patient treatment. Precise matching of the IVUS recordings at baseline and at 12 months will be performed and contour detection of both the lumen and external elastic membrane will be performed at approximately 1 mm intervals using validated software (QIVUS, v.3.0, Medis medical imaging systems, Leiden, the Netherlands). Borders will be reviewed by two independent operators according to the guidelines for acquisition and analysis of IVUS images by the American College of Cardiology and European Society of Cardiology.⁴⁴ The primary IVUS efficacy variable will be the mean change in the maximal intimal thickness between matched slices from baseline to 12 months as this parameter is an established predictor of all-cause mortality, myocardial infarction and angiographic abnormalities among HTx recipients.⁴² In accordance with established guidelines, the largest distance from the intimal leading edge to the

EEM is defined as the maximal intimal thickness.⁴⁴ Secondary IVUS variables are: (i) incidence of cardiac allograft vasculopathy (defined as mean a maximal intimal thickness \geq 0.5 mm over the entire matched segment) and (ii) normalised total atheroma volume.

7.1.2 Echocardiography

Top specified cardiac ultrasound devices will be used for echocardiographic imaging. Patients are examined in the lateral recumbent position after > 5 minutes of rest at baseline, and after 12 months. The heart is visualised by the standard ultrasonic techniques and imaging planes as recommended by the European society of echocardiography⁴⁵ providing a comprehensive hemodynamic and valvular assessment. In addition to apical recordings of the left ventricle, parasternal short axis cine loops at the mid-papillary level are recorded. Tissue Doppler examinations are performed from the three apical planes by using colour coding, and single pulsed Doppler at the septal and lateral mitral ring. Two-dimensional imaging from the apical position should be performed in the three standard planes in two imaging depths: One encompassing the ventricle(s) and atria, and one with the sector encompassing the left ventricle only, ensuring that the mitral plane is within the imaging sector throughout the cardiac cycle. Two-dimensional images should be optimised for speckle tracking analysis by 1) ensuring that 200 msec is recorded before and after each cine loop 2) keeping the frame rate above 50 frames/s and 3) ensuring that the sector encompasses the full thickness of the myocardium.

At least three heart beats (at least five in atrial fibrillation) are recorded with each registration. Recordings are performed before treatment and after 3 months, prior to study drug discontinuation. Blinded analysis of echocardiographic data will be performed off line using EchoPac (GE Vingmed). The following recordings should be obtained:

Projection:	Parameter:	
Parasternal long axis	Cine loop	Left ventricle
		Zoom LVOT (3 different recordings, only at
		baseline)
	M-mode	Mid left ventricular
	Colour Doppler	Left ventricular outflow tract
		Mitral valve
Parasternal short axis	Cine loop	Left ventricle at the level of the papillary
		muscle
		Left ventricle at mid-ventricular level
		Aortic valve
	Colour Doppler	Aortic valve and right ventricular outflow
		tract
Apical 4chamber / 5	Cine loop	Four-chamber including atria
chamber		Four-chamber zoom left ventricle*
		Four-chamber zoom right ventricle
	Colour Doppler	Mitral valve
		Aortic valve
		Tricuspid valve
	Doppler	Mitral valve tip (pulsed wave)
		Mitral regurgitation jet (continuous wave)
		Pulmonary vein (pulsed wave)
		Left ventricular outflow tract (pulsed wave)
		Aortic flow velocity (continuous wave)
		Tricuspid regurgitation jet (continuous wave)
	Tissue Doppler	Colour TVI left ventricle

		Colour TVI right ventricle
		TVI pulsed wave mitral annulus septum
		TVI pulsed wave mitral annulus
		anterolateral wall
Apical 2 chamber	Cine loop	Two-chamber including left atrium
		Two-chamber zoom left ventricle*
	Tissue Doppler	Colour TVI left ventricle
Apical long axis	Cine loop	Apical long-axis including left atrium
		Apical long-axis zoom left ventricle*
	Colour Doppler	Mitral valve
		Aortic valve
Apical long axis	·	Apical long-axis zoom left ventricle* Mitral valve

*Settings ideal for speckle tracking: Patient in breath-hold for three consecutive heart beats. Frame rate above 50 beats per min. The sector should include full thickness of ventricular wall. On the other hand, the left ventricle should fill entire sector (no "dead space"). Depth set so as to include mitral annulus at any time trough heart cycle. LVOT: Left ventricular outflow tract; TVI: Tissue velocity imaging.

7.1.3 Quality of life

Quality of life will be examined at baseline and at the end of treatment using three validated questionnaires; the SF36 (version 1)⁴⁶, the Beck's depression inventory, and the EQ 5D 3L EuroQoL questionnaires.⁴⁷ The SF-36v2 is a 36-item general health-related quality of life instrument that has 36 questions that contribute to 8 domains or scale scores of physical functioning, role-physical, bodily pain, general health, vitality, social functioning, and role-emotional and mental health.⁴⁶ The EQ 5D 3L EuroQoL questionnaire consists of 2 pages, the EQ-5D descriptive system and the EQ visual analogue scale. The Beck depression inventory is a 21-question multiple-choice self-report inventory for measuring the severity of depression. The test is rated on a 4-point scale ranging from 0 to 3 based on severity of each item. The maximum total score is 63.

7.1.4 Blood samples

We will collect fasting blood samples for biobanking at baseline, and at every subsequent visit. For biobanking, 18 ml blood should be collected in tubes containing EDTA, 6 ml in tubes with citrate and 6 ml in tubes without additives. The tubes with EDTA and citrate should be put on ice immediately and be centrifuged at 3700 rotations/min for 20 minutes. The tubes without additives should be left at room temperature for 1-2 hours prior to centrifugation at 3500 rotations/min for 15 minutes. The tubes containing citrate as the anticoagulant should be put on ice immediately. The resulting plasma and serum, respectively, should be stored in multiple aliquots (at least four aliquots of serum and six aliquots of plasma per patient per visit), and labelled with the unique trial subject number, and the letter A signifying baseline, and the letter B signifying the 1-month visit etc. The samples should be stored at -80 degrees Celsius until analysis.

Blood samples for safety will be collected at screening, and 1, 2, 3, 6, 9, and 12 months after randomisation. These blood samples will be collected and analysed at the study sites as per clinical routine. The glomerular filtration rate (in in ml/min/1.73 m²) will be estimated by the MDRD formula: $175 \times (SCr)-1.154 \times (age)-0.203 \times 0.742$ [if female] $\times 1.212$ [if black], where SCr is serum creatinine in mg/dl, and age is measured in years.⁴³ C-reactive protein, NT-proBNP, and troponin T-values will be used for endpoint analyses. Blood lipids must be assessed after end-of treatment only, to avoid what will effectively amount to study drug allocation unblinding. To avoid bias, the investigators will be blinded to the lipid analyses.

NT-proBNP will be assayed on a MODULAR platform (Roche Diagnostics, Basel, Switzerland). Plasma levels of CRP will be determined by a high-sensitivity particle-enhanced immunoturbidimetric assay (Tina-quant CRP [Latex] HS, Roche Diagnostic, Basel, Switzerland). TnT will be assessed using a high-sensitive immunoassay (Roche hs-TnT).

7.1.5 Biobanking

A dedicated biobank will be established at Oslo University Hospital, Rikshospitalet under the auspices of [name]. Blood samples for efficacy can be stored at each centre at -80 degrees in dedicated freezers until analysis. Blood samples for tertiary/exploratory efficacy analyses, including vasoactive peptides, markers of endothelial function and inflammatory markers, must be shipped to the core laboratory at Oslo University Hospital for analysis.

7.1.6 Cardiac microcirculation

In selected patients, we will perform a substudy where we perform measurements of the cardiac microcirculation. See Appendix B.

7.2 Safety and tolerability assessments

Safety will be monitored by the assessments described below as well as the collection of AEs at every visit. Significant findings that are present prior to the signing of informed consent must be included in the relevant medical history/ current medical condition page of the CRF. For details on AE collection and reporting, refer to Section 8.

For the assessment schedule, refer to Flow chart in Section 6.1.

Study-specific physical examinations will be performed at baseline and at 1, 2, 3, 6, and 12 months. Vital signs including heart rate and blood pressure will be recorded.

Blood samples for safety analyses will be drawn at baseline and after 1, 2, 3, 6, 9, and 12 months. Local laboratory cut-points for normal values will be used for safety analyses. Haemoglobin; white blood cell count, platelet count; serum potassium; serum sodium; glucose, glycosylated haemoglobin (HbA1c); creatinine; ALT; bilirubin; albumin; INR; CRP; TnT; and NT-proBNP. For the EVOLVD trial, we will not perform routine measurements of total cholesterol; LDL cholesterol, HDL cholesterol or other blood lipids for the duration of the treatment period. Instead, the biobank samples will be analysed regarding blood lipids retrospectively for efficacy and compliance assessments.

8 Safety monitoring and reporting

The investigator is responsible for the detection and documentation of events meeting the criteria and definition of an adverse event (AE) or serious adverse event (SAE). Each patient will be instructed to contact the investigator immediately should they manifest any signs or symptoms they perceive as serious. When judging whether an adverse event is unexpected or not, the Repatha[®] Summary of Product Characteristic (SPC) will be used as reference safety information.

The methods for the collection of safety data are described below.

8.1 Definitions

8.1.1 Adverse event (AE)

An AE is any untoward medical occurrence in a patient administered a pharmaceutical product and which does not necessarily have a causal relationship with this treatment.

An adverse event (AE) can therefore be any unfavourable and unintended sign (including an abnormal laboratory finding), symptom, or disease temporally associated with the use of a medicinal (investigational) product, whether or not related to the medicinal (investigational) product.

The term AE is used to include both serious and non-serious AEs.

If an abnormal laboratory value/vital sign are associated with clinical signs and symptoms, the sign/symptom should be reported as an AE and the associated laboratory result/vital sign should be considered additional information that must be collected on the relevant CRF.

8.1.2 Adverse events of special interest (AESI)

In general, AESIs are AEs that occur in categories of special interest with regard to determining the benefit/risk profile and overall safety of a drug. Whereas there have been no particular safety concern in the large, randomised, placebo-controlled trials involving evolocumab, the clinical experience with this drug outside of controlled trials is yet limited. In particular, we will monitor any pregnancy that may arise during the trial. However, pregnancies during the first year after heart transplantation are extremely rare, and we will demand that female participants of fertile potential use at least one highly effective method of birth control for the duration of the treatment phase. Immunosuppressants used after heart transplantation have a narrow therapeutic range and are sensitive to drug interactions. While there is no pharmacokinetic or pharmacodynamic reason to expect interactions with evolocumab, we will monitor levels of immunosuppressive drugs closely.

8.1.3 Serious adverse event (SAE)

Any untoward medical occurrence that:

- Results in death
- Is immediately life-threatening
- In itself requires hospitalisation or prolongation of existing hospitalisation
- Results in persistent or significant disability or incapacity
- Is a congenital abnormality or birth defect
- Is an important medical event that may jeopardise the subject or may require medical intervention to prevent one of the outcomes listed above.

Medical and scientific judgment is to be exercised in deciding on the seriousness of a case. Important medical events may not be immediately life-threatening or result in death or hospitalisation, but may jeopardise the subject or may require intervention to prevent one of the listed outcomes in the definitions above. In such situations, or in doubtful cases, the case should be considered as serious. Hospitalisation for administrative reason (for observation or social reasons) is allowed at the investigator's discretion and will not qualify as serious unless there is an associated adverse event warranting hospitalisation.

8.1.4 Suspected unexpected serious adverse reaction (SUSAR)

Adverse Reaction: all untoward and unintended responses to an investigational medicinal product related to any dose administered;

Unexpected Adverse Reaction: an adverse reaction, the nature or severity of which is not consistent with the applicable product information.

Suspected Unexpected Serious Adverse Reaction: SAE (see section 8.1.2) that is unexpected as defined in section 8.2 and possibly related to the investigational medicinal products. When judging whether a possibly study drug related serious adverse event is unexpected or not, the Repatha[®] SPC will be used as reference safety information.

8.2 Time period for reporting adverse events and serious adverse events

For each patient the he standard time period for collecting and recording AE and SAEs will begin at the start of study treatment and will continue for 30 day after end-of treatment (at which time approximately 30 days will have passed since the last study drug injection). We will proactively follow up all AEs and SAEs for each patient during the course of the study; events will be followed up to resolution, unless the event is considered to be unlikely to resolve due to the underlying disease. Every effort should be made to obtain a resolution for all events, even if the events continue after discontinuation/study completion. Mandatory reporting of new AEs ends 30 days after the end-oftreatment visit.

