The main objective of the EVOLVD trial is to assess the effect of evolocumab on measures of cardiac allograft vasculopathy. While conventional coronary angiography is performed per current routine in our heart transplant recipient several weeks after heart transplantation and again one year after heart transplantation, in the EVOLVD trial, we plan to perform the first angiography up to eight weeks earlier, if there is no contraindication to coronary angiography at this time. In conjunction with the conventional exam, we will perform intravascular ultrasound and, in a subset of the patients, analyses of coronary physiology. The latter examination is more thoroughly described in Appendix B. We have no reason to believe that advancing the baseline angiography puts our patients at increased risk of complications. The addition of the IVUS and microcirculation measurements will add approximately 30 minutes to the procedure. The added measurements are associated with a minimal increase in risk on top of the conventional angiography.³⁵

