6.2.2 Randomisation and Baseline Procedures (Day 1)

After confirmation of eligibility, baseline efficacy measurements can be made, and the online randomisation process can be performed. If more than 72 hours have passed since the screening visit, the physical exam should be repeated, vital signs recorded anew, and safety blood samples should be repeated.

Quality of life

Self-reported, health-related quality of life will be gauged with the SF-36, the Beck's depression inventory, and EQ 5D 3L questionnaires. We will allow subjects to complete the quality of life assessments before study procedures are performed.

Coronary angiography with intravascular ultrasound

Per routine, we perform coronary angiography approximately 12 weeks after heart transplantation to assess the allograft vessels. For the EVOLVD trial, we will ask the participants to have this "baseline" angiography within 4 to 8 weeks after heart transplant. The baseline IVUS, which is performed for study-specific purposes only, must be performed before study-specific treatment is started. We surmise that, to obtain the wanted effect on coronary artery intima thickness, aggressive cholesterol lowering treatment should start as soon as possible after heart transplantation. We therefore want to advance the baseline coronary angiography, so that it is performed shortly after enrolment.

Measurements of cardiac microcirculation (optional: See Appendix B)

In a subset of approximately 80 patients, we aim to assess cardiac microcirculation. For description of rationale and methods, see Appendix B.

Echocardiography

A comprehensive echocardiographic exam for study purposes must be performed prior to study drug administration. A copy of this exam will be stored in the clinical imaging archive under the patient's real name for reasons of safety.

Blood samples

Blood for efficacy analyses (specified later) must be collected, drawn and appropriately labelled and stored in a dedicated biobank for later analysis.

Randomisation

The randomisation code will be generated online on the eCRF (Viedoc®) platform

Study drug injection

The first study drug injection, starting on day 1, will be performed by a dedicated study nurse, who will also provide training for self-administration of the study drug.

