7.1.3 Randomisation and treatment allocation

Treatment is allocated according to a computer based balanced, permuted block randomisation (in a 1:1: ratio for the two study arms). Treatment allocation is performed online on a password-protected platform designed for study purposes (Viedoc™) once eligibility has been confirmed, the informed consent has been signed and baseline assessments have been performed. Randomisation is stratified by centre.

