9.2.3 Safety set

The safety set (SS) will include all patients who received any study treatment (including control) but excluding subjects who drop out prior to receiving treatment.

Each patient's inclusion or exclusion status regarding each analysis population must be determined prior to breaking the blind. The status must be documented in the final database prior to breaking the blind.

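### AE and SAE recording opens at the first dose, after the study-only baseline IVUS, so complications arising between consent and first dose have no clear recording or reporting rule

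*Protocol*

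**What the plan says.** - **Recording window.** Under Protocol 8.2 the standard period "will begin at the start of study treatment and will continue for 30 day after end-of treatment". The 12-month visit and the 30 days after it are inside.
- **Order of events.** Protocol 6.2.2: "The baseline IVUS, which is performed for study-specific purposes only, must be performed before study-specific treatment is started". About 80 patients may also have an optional microcirculation measurement. SAP 7.1.3 allocates treatment only when "the informed consent has been signed and baseline assessments have been performed", and SAP 7.1 has dosing follow directly.
- **Procedure risk.** Protocol 1.4 says of the routine angiogram that "we plan to perform the first angiography up to eight weeks earlier", and adds: "We have no reason to believe that advancing the baseline angiography puts our patients at increased risk of complications". On the IVUS and microcirculation work it says: "The added measurements are associated with a minimal increase in risk on top of the conventional angiography".
- **Definitions.** Protocol 8.1.1 describes an AE in a patient who has been given a product. Protocol 8.3 grades causality against study medication only. Protocol 8.4.1 sets the 24-hour SAE duty.
- **Before consent.** Protocol 7.2: "Significant findings that are present prior to the signing of informed consent must be included in the relevant medical history".
- **Population.** Protocol 10.3 requires at least one dose. SAP 9.2.3 counts treated patients, "excluding subjects who drop out prior to receiving treatment", and SAP section 12 reports safety on that set alone.
- **Passages pointing the other way.** The flow charts (Protocol 6.1, SAP 7.1.5) mark safety at pre-treatment and, in brackets, at baseline, and mark clinical events at baseline. Protocol 7.2 has AEs collected at each visit. Protocol 6.2.3 records events since the preceding visit. Protocol 6.2.4 and 6.2.5 review medical events since inclusion.

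**The concern.** The trial asks patients who are 4 to 8 weeks past transplantation to have an intracoronary examination for research purposes, on an angiogram moved forward for the same reason. The formal safety window opens only afterwards. The same examination at 12 months falls inside the window, so an acute complication is treated differently depending on which of the two procedures caused it.

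What is at stake is participant protection and SAE oversight. The sponsor's 24-hour notice and the safety committee's AE and SAE counts both depend on events being classed and reported as AEs or SAEs.

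**Working it through.** The plan gives no figure on this point, so the main check sets the passages side by side. The arithmetic at the end is for scale only.

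**Step 1. Where an event goes, by time of onset**

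| Onset | Stated place |
|---|---|
| Before consent | Medical history (Protocol 7.2) |
| Consent to first dose, including baseline angiogram and IVUS | No explicit rule in 7.2 or 8.2 |
| First dose to 30 days after end of treatment, including the 12-month IVUS | AE/SAE record (Protocol 8.2) |

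**Step 2. Do the other passages fill the middle row?**

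- *Flow-chart marks.* Sections 6.2.1 and 6.2.2 contain no safety-assessment item, whereas 6.2.3, 6.2.4 and 6.2.5 each do. The bracketed baseline marks for vital signs, physical examination and safety match the 72-hour repeat rule in 6.2.2, which covers vital signs, physical examination and safety bloods. The mark may therefore mean laboratory safety (an inference). If it means AE capture, it conflicts with 8.2.
- *AE collection at each visit (7.2).* The same paragraph refers to Section 8 for the details, and so to 8.2.
- *Month-1 look-back (6.2.3).* On its face it reaches back to the baseline visit, but it comes a month later and only for patients still in follow-up.
- *Month-12 and month-13 reviews.* These are medical-history items, up to a year after the procedure. They cannot serve a 24-hour duty, and they miss anyone who left before dosing.

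None of these settles the matter, so the documents are inconsistent.

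**Step 3. Who is outside the safety set?**

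The safety set is made up of patients, not events. A patient with a baseline complication who is later dosed belongs to it, although the pre-dose event precedes the 8.2 window. A patient who is never dosed is outside both.

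**Step 4. Scale**

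Inputs: n = 130 (Protocol 4.2), and p = the rate of baseline-procedure complications with onset before dosing. The documents give no value for p, so it is assumed.

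Expected events = n × p. Chance of at least one = 1 − (1 − p)^n.

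| Assumed p | Expected events | At least one |
|---|---|---|
| 0.1% | 130 × 0.001 = 0.13 | 12% |
| 0.5% | 130 × 0.005 = 0.65 | 48% |
| 1% | 130 × 0.01 = 1.3 | 73% |
| 2% | 130 × 0.02 = 2.6 | 93% |
| 3% | 130 × 0.03 = 3.9 | 98% |

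At each assumed rate the expected count is an upper bound on events without a clear rule, because some may be picked up through the passages in Step 2.

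**The case against.** The strongest reply is that 8.2 describes a standard period and need not be the only route. The 24-hour duty in 8.4.1 refers to 8.1.1, not 8.2. The SAE definition in 8.1.3 has no dosing condition. The unrelated grade in 8.3 allows for events that come too early or where no product was taken, so the form can hold a pre-dose event. Section 6.2.2 places the baseline procedures and the first injection under Day 1, so the interval may be short. Angiography is routine care that is only moved earlier, and the additions take about 30 minutes. For a patient who withdraws, 6.4.2 requires the reason and follow-up of significant adverse events, SAP 10.1 reports dropouts with reasons including death, and under 8.6 the safety committee can ask for more information.

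Much of this stands, and it rules out several stronger readings that a reader might infer:

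- *That such events would go wholly unrecorded.* The look-backs and the withdrawal rules may catch some of them.
- *That all complications of the trial's invasive procedures are outside the window.* Those of the 12-month IVUS, and baseline complications that appear after dosing, are inside.
- *That the safety comparison between arms is biased.* Under the SAP, baseline assessments precede randomisation, so the gap is unrelated to allocation.
- *That the trial thereby fails to test its own statement on procedure risk.* Procedure risk is not an objective, there is no comparison group with unadvanced angiography, and one to three events would not settle it.

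What does not stand is that the gap is closed. The reference from 8.4.1 to 8.1.1 leads back to a definition built on a patient who has been given a product. A short interval does not help with an acute complication, which arises during or soon after the procedure. A listing of dropouts is not an SAE report.

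**Conclusion.** The point holds in a limited form. As written, a complication with onset between consent and first dose has no clear AE/SAE recording rule and no clear 24-hour reporting rule, and a patient harmed and never dosed is also outside the safety set. The passages that suggest otherwise make the documents inconsistent without resolving the question.

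The consequence is for safety oversight and the reporting of procedure risk. It does not reach the efficacy analysis or the treatment comparison. The range of 0.65 to 2.6 events in 130 patients rests on an assumed 0.5% to 2% with onset before dosing, and is an upper bound at those rates. Severity is minor to moderate.

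**What to change.** 1. In Protocol 8.2, start recording and reporting of SAEs and study-procedure-related AEs at signed consent, before the baseline angiogram and IVUS.
2. Align 8.1.1 so that the AE definition covers a consented patient who has not yet been dosed. Changing 8.2 alone would leave the definition in conflict with the new window.
3. Add relation to study procedure to the causality item in 8.3.
4. Reconcile the flow chart in 6.1 (and its copy in SAP 7.1.5) and the text of 7.2 with the revised 8.2.
5. In the SAP, add a separate listing of pre-dose events for all consented patients, including those never dosed. Keep the treatment comparison on the safety set from first dose.

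The cost is wording changes and one extra listing. The patient is already registered in the eCRF at consent (Protocol 6.2.1). SAP 7.4 describes randomisation in the past tense, so prospective recording may come too late for some or all baseline procedures. In that case the listing can be compiled from the medical records described in Protocol 9.2, and labelled as retrospective.
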